NCT02994979

Title: "Multicomponent Intervention to Prevent Delirium in Nursing Homes"

Principal Investigator: [name]

Date of document: 11/11/2014

A. SIGNIFICANCE

A.1 Importance of delirium in nursing home patients

Delirium is frequent and adversely affects quality of life in older adults. Approximately one third of older adults hospitalized with acute medical problems experience delirium.^{1, 25-26} Delirium in nursing homes, as in hospital settings, is often precipitated by acute illness. Nursing home residents experience 2-4 acute illness episodes per year (e.g., respiratory, urinary tract, and gastrointestinal infections),²⁷⁻²⁸ and ¾ of these are managed in the nursing home. Studies show a delirium prevalence of 16-23% at the time of nursing home admission³⁻⁴ and up to 33% in nursing home long-term care,⁵⁻⁶ and a nearly universal presence of multiple delirium risk factors (one or more of: cognitive impairment, immobility, sensory impairment, and neuropsychiatric medication use).⁷⁻¹⁰ Delirium is reported to be an uncomfortable and traumatic experience by those who have experienced it – with acute distractibility, disorientation, hallucinations, and change in alertness – and for family witnesses.²⁹ In longitudinal studies of delirious nursing home patients these symptoms last for 1-9 weeks in those whose delirium remits, but 20% of delirious nursing home patients remain symptomatic past 24 weeks of follow-up.³⁰ Many nursing home patients who develop delirium do not return to their pre-delirium level of cognitive function.¹¹ Delirium in nursing home patients is a powerful risk factor for poor health outcomes. As compared to those without delirium, patients with delirium are more likely to die,⁵ be hospitalized or rehospitalized,¹² and less likely to be discharged home.¹² These adverse outcomes parallel the outcomes of hospitalized older adults with delirium, who have longer hospital stays, 2-3 fold higher mortality at 1 year, and increased risk of nursing home stays.³¹ Cognitive change indicative of delirium is a common reason for hospital transfer of nursing home patients.¹³⁻¹⁴ The association of delirium with increased hospital use drives excess costs, with total 1-year excess costs attributable to delirium between \$18,024 - \$71,221 per patient in 2014 dollars.¹⁵

A.2 Lack of existing approaches to delirium in the long-term care setting

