B.4 Preliminary studies. In addition to studies establishing our enrollment and assessment procedures,^{18, 49} we have conducted preliminary studies to demonstrate the feasibility of intervention procedures and acceptance by nursing home staff.²⁰ *First, we developed standardized procedures and training (Appendix 2) in collaboration with a HELP Center of Excellence. At start up and thereafter we instituted a weekly whole-team rounds and discussion of each patient to optimize intervention fidelity.* In 2013 we implemented the intervention during 149 acute illness episodes at the study site, for a rate of 14 per month. 63% of patients were female, 37% Spanish-speaking, with average age of 83 years. The mean Brief Interview of Mental Status score was 7.5 (max possible score 15), indicating moderate cognitive impairment. The most common illnesses initiating receipt of the intervention were infections of bladder (29%), lower respiratory tract (18%), and skin (10%). Intervention CNAs delivered on average 14.2 visits over a 13.5 day span per episode, with average visit length of 30.5 minutes. Patient adherence to each of the components per visit ranged from 70-94% (Table 1), with a goal of 75%. The most common reasons for not receiving a component were patient refusal and patient off floor or unavailable. In a semi-structured interview of 28 patients who were capable of providing feedback, 27 had high satisfaction with the intervention and endorsed the value of each intervention component. *On days when 2 CNAs visited the same patient (n=179), percent agreement on provision of the key intervention components (orientation, mobility, fluids) was high, ranging from 80-93%, indicating excellent fidelity.* Among 4 physicians and 13 unit nursing staff who participated in a semi-structured interview, all indicated that communication between unit and intervention staff was effective and 14 endorsed that work stress was lower with the intervention, indicating good integration between intervention and unit nursing activities. *Staff*

indicated that they appreciated and recognized the intervention CNA as a mobile staff member who delivered focused services to patients on the floors, but not daily care. Delirium occurred during 22% of acute illnesses and 5% of patients were transferred to the hospital during or within 30 days after finishing the intervention.²⁰

B.5 Investigative team

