C.4 Intervention and control. Residents with acute illness on intervention units will be seen by an intervention CNA at least once daily 7 days a week. The CNA will be English/Spanish bilingual and will provide intervention components as shown in Table 1 guided by structured protocols and a daily visit form (Appendix 2). A typical visit lasts 30 minutes and begins with an introduction and orientation activity followed by provision of water, a reminiscence activity or game, a physical exercise, and a snack and second cup of water. Patients may also receive a relaxation visit at night and given a warm drink, a hand or foot massage, and quiet music. Daily visits will last for the duration of the illness and 7 days following the illness end. Illness end is defined as the last day of illness treatment (e.g., last day of antibiotics) or monitoring (e.g., last day on nursing “24-hour report”). Seven day a week coverage, provided by 1.4 FTE CNAs, is important for this intervention since it is a relatively brief (e.g., 2 week) intervention. Medication review using American Geriatrics Society Beers criteria⁶³ for drugs associated with delirium will be semi-automated and alerts provided to the primary team by secure messaging or telephone. During weekly intervention staff meetings patients in the intervention group will be discussed with the primary medical and nursing team. The planned intervention group sample size results in a caseload of 4-8 patients seen daily, which is well within the workload capacity of the intervention CNAs. Patients with acute illness on control units will be cared for as usual by the primary nursing home nursing and medical staff.

Table 1. Intervention components: all components delivered by the CNA except for medication alerts

Risk Factor	Intervention	Recipients / Tailoring	Evidence	Adherence*
Cognitive Impairment	1) Daily visit & orientation activity 2) Therapeutic activity: reminiscence, reading, music, pictures	All patients.	1) Cognitive impairment is delirium risk factor ⁸⁻¹⁰	94% (79 off floor or unavailable; 23 refusals)
Immobility	Mobilization protocol performed to patient's maximum ability: 1) chair stands 2) walking 3) range of motion	All patients. Patient's maximum determined by intervention CNA from chart, patient and staff report, and observation	1) Early mobilization effective ¹⁹ 2) NH delirium assoc w/restraints ⁶⁴ 3) Delirium assoc w/fall ⁶⁵	77% (382 refusals; 80 off floor or unavailable)

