Dehydration	Hydration protocol: two 6-ounce cups of fluid by mouth daily	All patients except if not indicated as per nursing or medical team; e.g., those with congestive heart or renal failure with or at risk for fluid overload	1) Dehydration is delirium risk factor ^{64, 66} 2) Hi pulse & low BP assoc w/delirium ⁶⁵ 3) Rehydration may be effective ^{19, 34}	86% (178 refusals; 80 off floor or unavailable; 25 medical contraindicat)
Undernutrition	1) Provision of snack 2) Meal assistance	All patients receive snack unless 15 min before or after a meal	Undernutrition associated with delirium ⁶⁷	70% (385 refusals; 81 off floor or unavailable)
Sleep/relaxation	Sleep and relaxation protocol: massage, warm drink, quiet music	Patients who report sleep difficulties to intervention team	Avoiding sedative effective ¹⁹	80% (34 off floor /unavail; 12 time limit)
Medications	Medication alerts to medical team of meds associated w/delirium	All patients.	1) AGS criteria meds assoc w/ delirium ⁶³ 2) Med review effective ³⁵	--

*Per visit adherence data during 2434 visits, with top reasons patient did not receive a component.

C.5 Outcomes and variables. For intervention and control patients, a trained RA will use the Confusion Assessment Method (CAM), a widely-used, validated measure,⁵⁷ to ascertain incident delirium each weekday during treatment of the acute illness and for 7 days afterward. Delirium severity will be ascertained using the Delirium Index (DI), which has been shown to be reliable in patients with and without underlying dementia and its validity tested in a nursing home population.^{6, 58} Cognitive and physical function will be ascertained using the nursing home Minimum Data Set (MDS) Cognitive Performance⁶⁸ and Activities of Daily Living⁶⁹ scales, and the Brief Interview of Mental Status⁷⁰ at illness onset and 1 month after illness onset. These scales have been tested in the nursing home population and they are performed quarterly in all Medicare-certified facilities, making it possible to collect values on these measures from the medical record and establishing a pre-acute

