illness baseline. The RA will collect data by medical record review on demographic and clinical characteristics, characteristics of the acute illness, delirium risk, and hospital use (Table 2). Spanish language versions of cognitive test items have been obtained from developers of the delirium and cognitive instruments whenever available. We have developed Spanish versions of other items by iterative translation and back-translation.

Table 2. Outcomes and variables

Data	Source	Instrument or Measurement	Frequency or time point
Outcomes			
Delirium and delirium severity	Research assessment	Confusion Assessment Method (CAM); ⁵⁷ Delirium index (DI) ⁵⁸	Weekdays during illness & for 1w after illness end
Cognitive functional decline	Medical record, research assessment	Minimum Data Set Cognitive Performance scale; ⁶⁸ Brief Interview of Mental Status ⁷⁰	Pre-illness assessment, illness onset, illness end, 1m after illness onset
Physical functional decline	Medical record, research assessment	Minimum Data Set Activities of Daily Living scale ⁶⁹	Pre-illness assessment, illness onset, illness end, 1m after illness onset
Hospital use	Medical record	Hospital admission	Between illness onset & 1m after illness onset
Descriptive			
Demographics	Medical record	Age, gender, race/ethnicity	Enrollment baseline
Chronic illness	Medical record	14 chronic conditions (count)	Enrollment baseline
Acute illness	Medical record	Diagnosis and severity (Severity Score ⁷¹)	Acute illness onset
Delirium risk	Medical record; research assessment	Delirium risk score (↓vision, cognitive impairment, severe illness, ↑BUN/creat) ⁹	Acute illness onset
Intervention components received	Elder Life Specialist visit form	Component implemented that was indicated; reasons not implemented	During acute illness (intervention group only)
Intervention "dose"	Elder Life Specialist visit form	Frequency (n) of Elder Life Specialist visits; duration (min) of visits	During acute illness (intervention group only)

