C.6 Power and effect size. Based on our previous studies and the known impact of HELP on delirium,¹⁹ we hypothesize observing a clinically meaningful 40-60% relative reduction in new delirium from 35% to between 15% and 20%. Power calculations have been performed treating delirium as a binary (CAM) and continuous (DI) outcome and accounting for clustering of observations by unit and for correlations over time. For the binary variable, new delirium is defined as when delirium occurs any time during the illness period. Sample size was calculated (Figure 1) with the continuity correction,⁷²⁻⁷³ with assumed reliability (R)=.72; groups (g)=2; cluster size (by unit)=18; intraclass correlation (ICC)=.01; and variance inflation factor (VIF)=1+(cluster size-1)*ICC=1.17. With $\alpha=.05$ and ρ (estimated average correlation of the outcome measures over time)=0.60, a sample size of 150 per group will provide 80% power to detect a group difference in new delirium from 35% (baseline)

$$\text{Figure 1. } n' = \frac{(z_{\alpha/2} \sqrt{2P\bar{Q}} + z_{\beta} \sqrt{P_1Q_1 + P_2Q_2})^2}{(P_2 - P_1)^2}; n = \frac{n'}{4} \left(1 + \sqrt{1 + \frac{4}{n'(P_2 - P_1)}} \right)^2, \text{ where } \bar{p} = \frac{1}{2}(p_1 + p_2) \text{ and } \bar{q} = 1 - \bar{p}$$

to 18% (intervention). If the usual care group also has a small reduction in delirium to 30%, with 150 per group it will be possible to detect a reduction to 13.5% in the intervention group, a 55% relative reduction. Thus, 150 subjects per intervention group will provide sufficient power to detect the hypothesized difference between groups. Power was also examined using the sample size formula for the log-rank test. Assuming a VIF of 117%, $\alpha=.05$, and $\rho=.60$, given the same scenarios as above, with a sample size of 150 per group and power 80%, the detectable λ (hazard ratio) is 2.9. For the continuous

measure (DI), power calculations are based on an assumed σ (population pooled standard deviation) of 3.12, using data from our previous study. The effect size estimate is: δ (DI group difference) and $d = \delta/\sigma$ (where d is Cohen's d). Adjusting for clustering and reliability, the detectable endpoint difference with

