C. 7. Analysis Aim 1: The primary analysis for the binary outcome will be logistic regression (SAS, PROC GLIMMIX) to test the hypothesis that those assigned to the intervention will have significantly lower rates of delirium compared to those assigned to usual care. The clustering design effect will be modeled. The need for inclusion of covariates resulting from examination of potential sources of bias will be determined. Predicted values from these analyses will be included as covariates in the logistic regression analyses, if necessary. The continuous DI variable will be examined using slope analyses and the repeated measures ANCOVA model in SAS PROC MIXED. This method will allow for more flexible modeling of assumptions, treatment of missing observations and inclusion of all subjects with at least one wave of data, and the inclusion in the analysis of participants who do not complete follow-up assessments (on an ITT basis). Aim 2: The primary analysis for the binary outcome will be logistic regression to test the hypothesis that characteristics of the intervention (e.g., longer visits, components delivered) will be associated with less delirium, using only the intervention group sample and adjusting for covariates as needed to correct for imbalances, since in this case exposure is not assigned. Similar to Aim 1, the clustering design effect will be modeled. The continuous DI variable will be examined using slope analyses and the repeated measures ANCOVA model in SAS PROC MIXED. **Bias and missing data:** We do not expect significant drop-out in this study since it was not observed in our prior study with the 1-month follow-up period. **Attrition bias:** We will use baseline assessment information to compare completers and dropouts with regard to sociodemographics and other covariates. A logit model of attrition will be developed and the predicted values from this model used as a covariate to adjust for differential attrition. **Treatment of missing data:** Using the maximum-likelihood approach we will include baseline data, and we will try to obtain follow-up data from all randomized patients so non-completion will not result in loss to follow-up.

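### Aim 2 does not require visit length and components delivered to be measured before delirium starts, so an effect of delirium on delivery could be read as an effect of delivery on delirium

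*Combined protocol and SAP*

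**What the plan says.** Section C.7 gives Aim 2 a logistic regression within the intervention arm, on the hypothesis that "characteristics of the intervention (e.g., longer visits, components delivered) will be associated with less delirium, using only the intervention group sample". The safeguard offered is "adjusting for covariates as needed to correct for imbalances, since in this case exposure is not assigned".

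The timing of exposure and outcome has to be pieced together from other sections:

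- **Outcome.** In C.6, "new delirium is defined as when delirium occurs any time during the illness period". Under C.5 the research assistant is to "ascertain incident delirium each weekday during treatment of the acute illness and for 7 days afterward".
- **Exposure.** Table 2 records visit frequency and minutes, and for components "Component implemented that was indicated; reasons not implemented". The time frame for both is the acute illness. No rule says how a patient's visits are to be summarised.
- **Visits.** C.4 states: "Daily visits will last for the duration of the illness and 7 days following the illness end". There is no cut-off at delirium onset.

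On why components are missed, B.4 reports: "The most common reasons for not receiving a component were patient refusal and patient off floor or unavailable".

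**The concern.** A regression of outcome on exposure says something about prevention only if the exposure comes first. Here a patient who becomes delirious early goes on being visited, and those later visits can count towards the exposure that is then used to explain the delirium.

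It is plausible that delirium alters later delivery. Several components need the patient's cooperation, and A.1 describes the condition as presenting "with acute distractibility, disorientation, hallucinations, and change in alertness". A.1 also puts symptom duration at 1-9 weeks in those who remit, against an average pilot visit span of 13.5 days (B.4), so many visits after onset could be affected.

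What is at stake is the reading of Aim 2. C.9 anticipates that component findings may prompt changes to the intervention, so an association created by reverse causation could steer the redesign.

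**Working it through.** **Plan's own figure.** The documents give no power, sample size or effect size for Aim 2, so there is nothing to reproduce.

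**How the bias arises.** Take a patient with 14 visits, delivery at 77% per visit (the pilot mobility figure in Table 1) and onset after visit 4. If delivery then falls by a relative 20%, the whole-episode average is

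0.77 × (4 + 10 × 0.8) / 14 = 0.77 × 12/14 = 0.66.

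The 11-point shortfall against 0.77 arises entirely after onset.

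**Simulation with no true effect of delivery.**

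- *From the documents:* 153 intervention patients (C.1); delirium 18% (C.6) or 22% (B.4); mean 14.2 visits and 30.5 minutes per visit (B.4); 77% delivery (Table 1); alpha 0.05, taken as two-sided.
- *Assumed:* onset after visit 1 to 7; between-patient delivery Beta with mean 0.77 and precision 8; visit-length SD 5 minutes between and 8 within patients; the change after onset; the whole-episode average as exposure. Clustering was omitted (the stated ICC is .01).
- *Runs:* 600-800 per scenario, so the Monte Carlo standard error is at most √(0.5 × 0.5/600) = 0.020.

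Results for components delivered:

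| Relative change in delivery after onset | Median OR per 10 points | False protective finding | False harm |
|---|---|---|---|
| none | 0.98-1.01 | 2-3% | 2-3% |
| 5% fall | 0.92-0.93 | 10-12% | 0.3% |
| 10% fall | 0.84-0.86 | 27-35% | 0% |
| 20% fall | 0.72-0.74 | 77-87% | 0% |
| 30% fall | 0.63-0.65 | 96-99% | 0% |
| 10% rise | 1.17-1.19 | at most 0.2% | 26-28% |

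The nominal rate in each direction is 2.5%.

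For visit length, visits 2, 4 or 6 minutes shorter after onset gave ORs per 5 minutes of 0.79-0.80, 0.63 and 0.50-0.51, with false protective findings in 23%, 66-72% and 94-96%. Visits 2 minutes longer gave 1.24-1.26 and false harm in 21-24%. For number of visits, which C.1 also names, 3 extra visits in delirious patients gave an OR of 1.26 per visit and false harm in 97-99%.

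**Different assumptions.** With 80% mean delivery, onset uniform over the span and absolute falls of 10, 20 or 30 points, the two-sided 5% test rejected in 23-54%, 63-98% and 93-100% of trials, and in about 4-5% with no fall. Adding illness length as a covariate changed these rates by at most 0.004.

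**Exposure placed before outcome.** In the first set-up, with falls of 0-30%:

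- Landmark on the first 3 visits, patients still delirium-free: OR 1.00-1.01, false protective finding 2-4%.
- Discrete-time model with lagged exposure: OR 1.00-1.01, false protective finding 2-3%.
- Simple average of each patient's pre-onset visits, for components: OR about 1.0, but two-sided error about 11-17%, because cases then contribute few visits.

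These runs took the onset visit as known exactly; weekday-only CAMs will locate it less precisely.

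**The case against.** The strongest reply is that the mechanism is supplied from outside the plan. C.7 and Table 2 do not say that exposure is averaged over the episode, and the per-visit percentages in Table 1 only describe the pilot. Refusals and visit lengths are nowhere split by delirium status. Refusal leads for mobility (382 against 80 absent or unavailable) and snacks (385 against 81), but for orientation absence leads (79 against 23 refusals), and for sleep visits refusal is not among the listed reasons. B.2 presents mobile staffing as a way to move effort towards patients in need, so delivery could rise after onset. C.7 also speaks of association and admits that exposure is not assigned.

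All of this stands as a limit on what can be claimed. A reader might infer that Aim 2 will find a false benefit because delirious patients refuse more and engage less. The documents do not support that: A.1 lists symptoms, not cooperation with visits, and both the existence and the sign of any change after onset are assumptions. The rejection rates above are conditional illustrations, not forecasts.

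The reply does not close the gap. An unstated summary rule leaves the exposure window open, and acknowledging unassigned exposure deals with confounding, not with exposure altered by the outcome.

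**Conclusion.** The point holds in this form: as written, Aim 2 allows exposure to follow outcome, and the planned covariate adjustment cannot correct that. Any change in delivery caused by delirium would produce an association without a preventive effect.

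Direction and size are not determined by the documents. More refusal or shorter visits after onset, which is plausible but assumed, would favour the Aim 2 hypothesis; greater delivery would point to harm. Under the stated assumptions even a 5% relative fall raises the false protective rate about fourfold over nominal. With no change there is no distortion.

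The randomised Aim 1 comparison does not use these exposures and is unaffected. This is an inexpensive improvement to a secondary question, not a threat to the trial's main result.

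**What to change.** In C.7, Aim 2, state that exposure must precede outcome.

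- **Preferred:** a discrete-time model of first positive CAM, with visit length and components delivered lagged to visits up to the last negative CAM. Censor follow-up at the first positive CAM. Exclude patients CAM-positive at enrolment: C.2 lists no such exclusion, and they would have only post-onset visits.
- **Alternative:** a landmark analysis using the first 3 visit days among patients still CAM-negative, related to delirium found later. Set the landmark at a weekday CAM, since none is done at weekends.
- Do not use a simple pre-onset average. Report whole-episode delivery descriptively only.

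The daily visit forms and weekday CAMs already supply the timing, so the cost is wording, modest programming and lower precision. Expected events are about 0.18 × 153 = 27.5, say 28. The landmark loses 3/13.5 = 22% of them if onset is uniform over the span (leaving about 22). If onset is uniform over the first 7 visits it loses 2/7 = 29% to 3/7 = 43%, depending on how the boundary is treated (leaving about 20 to 16). The lagged model loses fewer. Neither removes ordinary confounding, so the covariate adjustment should stay.

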The PI has conducted innovative research to improve care in nursing homes, including interventions with CNAs, that has been widely cited and adopted.^{28, 59-60} He has worked with nursing homes in New York and nationally to implement innovative models of care. [name] (co-investigator) is the developer of HELP and the Confusion Assessment Method measure, and brings practical clinical trial experience.^{19, 57} [name] (Data Coordinating Center lead) has extensive experience in nursing home based research, measurement, and oversight of analyses from clinical studies.⁶¹ Advisory group members have been selected who provide expertise in the areas of delirium ([name]), nursing home ([name]), and long-term care nursing ([name]).

C. APPROACH

C.1 Overview. We propose to perform a controlled trial of a multicomponent intervention to prevent delirium at a large nursing home in New York City. The trial will be randomized by unit and evaluator-blinded. We will randomly assign 17 long-term care units to intervention or control and screen nursing home patients on each unit who experience onset of an acute change in condition according to established criteria and enroll 306. Those assigned to intervention (n=153) will receive daily visits from a mobile CNA trained to provide services to counter established risks for delirium, including dehydration, immobility, cognitive impairment, undernutrition, and sleep problems, for the duration of the acute illness and for 1 week following, in collaboration with the patient's primary medical and nursing team. Patients assigned to control (n=153) will receive usual care from the unit-based team. Delirium will be assessed 5 days a week by a research assistant (RA) blinded to study hypotheses and group assignment. Cognitive and physical function decline and hospital transfer will be ascertained during a 1 month follow-up period. We will conduct analyses to compare outcomes between intervention and control, as well as examine associations between outcomes and intervention features such as number and duration of visits. We will use regression models to adjust for covariates and effects of clustering.

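### Aim 2: raw visit count rises with time at risk, so it can look harmful with no dose effect unless it is turned into a rate and illness length is adjusted for

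*Combined protocol and SAP*

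**What the plan says.** C.7 makes Aim 2 a logistic regression confined to the intervention arm. Its examples of intervention characteristics open with longer visits, and the sentence runs on: "components delivered) will be associated with less delirium, using only the intervention group sample and adjusting for covariates as needed to correct for imbalances". The reason given is that exposure is not assigned here. No covariate is named. Unit clustering is to be modelled as in Aim 1.

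Visit number is not among the C.7 examples. It comes from C.1, which intends to "examine associations between outcomes and intervention features such as number and duration of visits", and from Table 2, where dose is "Frequency (n) of Elder Life Specialist visits; duration (min) of visits" with the time point "During acute illness (intervention group only". Components are recorded as "Component implemented that was indicated; reasons not implemented".

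On the schedule, C.4 states "Daily visits will last for the duration of the illness and 7 days following the illness end" and "Illness end is defined as the last day of illness treatment (e.g., last day of antibiotics) or monitoring". C.5 and Table 2 put CAM assessments on weekdays over that same span. C.6 instead defines the binary outcome as delirium at any time in the illness period.

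Table 2 describes the acute illness by "Diagnosis and severity (Severity Score", taken at onset, and lists a delirium risk score, also at onset. Illness length is not listed as a variable, although illness onset and illness end both appear as time points for the cognitive and physical function measures.

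**The concern.** With daily visits, the number of visits is set largely by how long the illness lasts. So is the number of days on which delirium can occur and be detected. An ever/never outcome regressed on a raw count then compares long illnesses with short ones. Patients with more visits will tend to have more delirium even if a visit does nothing, and the result reads as harm from a higher dose. Total minutes and total components behave the same way.

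The covariate clause would allow an analyst to remove this, but the covariates in Table 2 are measured at enrollment or illness onset and are only partial stand-ins for illness length. At stake is the dose reading of the trial. C.9 expects that findings on components may lead to changes in the intervention. That sentence is about components rather than visit count, so the link to count is indirect, but a spurious finding that more visits go with more delirium would feed the same decision.

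**Working it through.** The documents state no sample size, power or effect size for Aim 2, so there is no planned figure to reproduce.

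**Inputs from the documents.** Intervention arm n = 153 (C.1). Pilot mean of 14.2 visits over 13.5 days, and delirium in 22% of episodes (B.4). Planned intervention-arm rate 18%, ICC .01 (C.6). Visits for illness plus 7 days (C.4).

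**Derived.** Visits per day = 14.2 / 13.5 = 1.05. Mean illness length = 13.5 − 7 = 6.5 days, taking the pilot schedule to be the same.

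**Assumed, because not given.** Spread of illness length and timing of delirium onset.

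**Step 1: hand calculation, constant daily risk, no dose effect.** Compare a 3-day with a 10-day illness. Visits: (3 + 7) × 1.05 = 10.5 and (10 + 7) × 1.05 = 17.9.

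- Illness-only window: h = 1 − (1 − p)^(1/6.5). For p = 18%, h = 0.0301 and the risks 1 − (1 − h)^3 and 1 − (1 − h)^10 are 8.8% and 26.3%; odds ratio 3.7. For p = 22%, h = 0.0375 and the risks are 10.8% and 31.8%; odds ratio 3.85.
- Illness plus 7 days: h = 1 − (1 − p)^(1/13.5), with 10 and 17 days at risk. For p = 18%, 13.7% and 22.1%; odds ratio 1.79. For p = 22%, 16.8% and 26.9%; odds ratio 1.82.

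If risk is confined to the first 7 days, every patient's illness-plus-7 window covers all of it, so the odds ratio on that window is 1. On the illness-only window a 3-day illness covers 3 risk days and a 10-day illness 7, so a difference remains.

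**Step 2: null simulations.** 153 patients in 8 units, mean illness 6.5 days, 20–24% delirious, weekday CAM, 1,000 trials per setting. Percentage of trials in which raw visit count was significantly harmful (nominal 2.5%), by assumed SD of illness length:

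| Outcome window and onset timing | SD 5 | SD 4 | SD 2.3 | SD 1.1 |
|---|---|---|---|---|
| Illness + 7 days, constant risk | 48 | 34 | 12 | 4 |
| Illness + 7 days, fading risk or first 3, 5 or 7 days only | 2–4 | 2–4 | 2–4 | 2–4 |
| Illness only, constant risk | 97 | 92 | 41 | 12 |
| Illness only, fading risk | 31 | 33 | 12 | 5 |
| Illness only, first 7 days | 53 | 53 | 21 | 8 |
| Illness only, first 3 days | 8 | 12 | 3 | 2 |

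Repeating the constant-risk runs with separate code gave 11–31% (CAM window) and 39–90% (illness only) over SD 2.3–4; hence the combined ranges 11–34% and 39–92%. A variant with lognormal illness length and noisier visit counts gave, on the illness-only window, a median odds ratio per 7 visits of 1.20–1.22, 1.41–1.45 and 1.63–1.69 at coefficients of variation 0.3, 0.5 and 0.8, with false harm in 10–12%, 29–36% and 73–83%.

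**Step 3: do the listed onset covariates suffice?** With the risk score plus a severity score correlated 0.3, 0.5 or 0.7 with illness length (SD 4, constant risk), false harm was still 33%, 27% and 18% on the CAM window and 92%, 80% and 57% on the illness-only window.

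**Step 4: alternatives under the same null.** Count with illness length as covariate: 4–6% total error (nominal 5%). Visits per day: 2–5% total error. Mean minutes per visit: 3–6%. Share of indicated components: 4–6%. Total minutes stay biased (odds ratio 1.31–1.53 in the lognormal variant, illness-only window).

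**Step 5: a raw count cut at delirium onset.** Cases are truncated early, so the count looks protective in over 99% of null trials (odds ratio per 7 visits about 0.01–0.20).

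**The case against.** **Scope.** The two exposures named in the Aim 2 sentence escape the problem when expressed per visit or as a share. Visit count sits in an overview and under the descriptive rows of Table 2, and nothing says that it enters unadjusted. This stands as a limit: a reader might infer that Aim 2 as a whole is invalid, and the documents do not support that. It does not remove the point, because C.1 states the intention to relate outcomes to visit number and no rate or time-at-risk term is committed to.

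**Data.** A reader might infer that illness length is unavailable. It is not: C.4 defines illness end and Table 2 schedules assessments at onset and end. This makes the fix cheap.

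**Size.** The simulated range is wide, and B.1 treats acute illness as the precipitant, which makes early onset plausible. On the CAM window, early risk leaves no bias. This stands. On the illness-only window suggested by C.6, risk limited to the first 7 days still gave 21–53% at SD 2.3–4 (19–37% on a repeat with separate code).

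**Illness length is measured after baseline.** Delirium might itself prolong monitoring and hence illness length and visits. How often is not stated, so it cannot be claimed to happen. In a run where it added an assumed 2 days, visits per day kept false harm at 2.3% and count adjusted for length at 2.7%, against 83% for raw count. This favours a rate over a count that relies on the covariate alone.

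**Falling uptake.** A reader might also infer that delirious patients refuse more, so that component share looks falsely protective. Table 1 pools all visits and does not split refusals by delirium status, so this is conjecture. It justifies an optional sensitivity analysis only.

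**Delirium Index.** Aim 2 also has slope and repeated-measures models for severity. Repeated scores do not accumulate with time at risk as an ever/never outcome does, and the point is not extended to them.

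**Conclusion.** The point holds for raw visit count, and for totals of minutes or components, in the Aim 2 logistic model. Visit count is planned as a dose measure, it shares illness length with the outcome, and the covariate clause permits the needed adjustment without committing to it. The sizes in the brief rest on constant daily risk and an illness-length SD of 2.3–4 days. They shrink towards nominal if illness length varies little (4% and 12% on the two windows at SD 1.1) and vanish on the CAM window if risk is early. Since neither spread nor timing is documented, the actual bias cannot be estimated; its mechanism and remedy do not depend on it.

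The randomised comparison in Aim 1 is not affected. Aim 2 is an observational analysis within one arm, so this should be settled before that analysis is run but does not threaten the trial's main result.

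**What to change.** In the Aim 2 logistic model:

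- Replace raw counts and totals with visits per day of the visit period (illness length plus 7 days), mean minutes per visit, and the share of indicated components delivered. Say whether night relaxation visits are counted.
- State one outcome window, since C.5 and C.6 differ.
- Name illness length (from recorded illness onset and illness end) and the baseline delirium risk score as covariates, and keep the planned unit clustering term.

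Optionally, add a sensitivity analysis that limits the rate or share to the time before delirium onset, in a daily model adjusted for day since illness onset, because dose after onset could reflect the delirium itself. Do not use a raw count cut at onset.

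The cost is a few lines of text and a little programming; the visit form and weekday CAM already supply the data. The optional analysis has less power. In simulation with an assumed between-patient uptake SD of 9 points and a true odds ratio of 0.5 per 10 points, a pre-onset model of component share had 31–62% power against 82–88% for the whole-period analysis. It should therefore not be the sole analysis.
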